9.3. Statistical analysis stages and timeline for reports

The analysis of the results in this clinical trial will be performed upon receipt of all the data planned by the Protocol of the last volunteer included in the study.

9.4. Criteria for study termination

JSC BIOCAD may temporary or permanently stop the study due to issues related to safety, ethics, adherence to protocol, or other reasons. If necessary, JSC BIOCAD will undertake the necessary measures to inform the study site in advance. If the study is temporary or permanently closed, JSC BIOCAD and the Investigator must inform the Ethics Committees and regulatory authorities. In such cases, all study-related data must be submitted to JSC BIOCAD and all unused study drugs must be returned.

9.5. Management of missing, non-evaluable, and uncertain data

[REDACTED]

Translated from Russian to English, dated 06-Jul-2020

9.6. Procedures for reporting any deviations from the initial statistical plan

If the initial clinical study plan must be changed, modifications will be described and explained in the protocol amendment or Interim/Final clinical study report.

9.7 Patient selection for analysis

Demographic data and baseline clinical and laboratory characteristics will be evaluated in all volunteers included in the study.

Safety analysis

Safety analysis will include all volunteers who received the test drug.

Pharmacokinetic analysis

Pharmacokinetics analysis will include data from volunteers who have received BCD-089 and have had no more than two missing/lost/damaged blood serum samples for pharmacokinetics and had no more than two consecutive missing/lost/damaged samples and for whom a serum sample obtained before the test drug administration is available for the analysis.

Pharmacodynamic analysis

Pharmacodynamics analysis will include data from volunteers who have received BCD-089 and have had no more than two missing/lost/damaged of whole blood and/or blood serum for pharmacodynamics studies, and for whom a serum sample obtained before the test drug administration is available for the analysis.

Immunogenicity analysis

Immunogenicity analysis will include data from volunteers who have received BCD-089 and have not had missing/lost/damaged serum samples taken on Days 1 and 71 of the study.

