4.6. Description of sequence and duration of all study periods

4.6.1 Schedule of study visits and procedures

The schedule of visits and their conduct are similar for the volunteers in all cohorts. A 14-day screening examination and 13 subsequent visits are planned to be conducted during the study. The first day of the study is the day of the first administered of BCD-089. The subsequent visits are calculated relative to the first BCD-089 administration. The frequency and timing of the study procedures are shown in Table 7.

Table 7. Listing and frequency of investigations and clinical examinations.

Study type	Control parameters	Frequency

[REDACTED]
 
[REDACTED]
 
[REDACTED]
	
[REDACTED]
 
[REDACTED]
 
 • [REDACTED] 	
[REDACTED]

[REDACTED]
	
 • [REDACTED] 	
[REDACTED]
 
[REDACTED]
 
[REDACTED]
 
[REDACTED]
 
[REDACTED]
 
[REDACTED]
 
[REDACTED]
 
[REDACTED]
 
[REDACTED]

[REDACTED]
 
[REDACTED]
	
 • [REDACTED] 	
[REDACTED]

[REDACTED]
 
[REDACTED]
	
 • [REDACTED] 	
[REDACTED]
 
[REDACTED]

Translated from Russian to English, dated 06-Jul-2020

Study type	Control parameters	Frequency

[REDACTED]
	
[REDACTED]
 
 [REDACTED] 	
[REDACTED]

[REDACTED]
	
 [REDACTED] 	
[REDACTED]

[REDACTED]
	
 [REDACTED] 	
[REDACTED]

[REDACTED]
	
 [REDACTED] 	
[REDACTED]

[REDACTED]
	
[REDACTED]
 
 [REDACTED] 	
[REDACTED]

[REDACTED]
	
 [REDACTED] 	
[REDACTED]

Translated from Russian to English, dated 06-Jul-2020

Table 9. Study flowchart.

Visit number	screening	1	2	3	4	5	6	7	8	9	10	11	12	13
Visit		Day 1	Day 2	Day 3	Day 4	Day 5	Day 6	Day 8	Day 11	Day 15	Day 22	Day 29	Day 50	Day 71
Day from the first injection	-14	0	1	2	3	4	5	7	10	14	21	28	49	70
Signing the Informed Consent Form	+													
Clinical and demographic data collection	+													
Assessment of vital signs	+	+ ²						+		+	+	+	+	+
Height measurement	+													
Body weight measurement	+	+												
Physical examination	+	+						+		+	+	+	+	+
Chest photofluorography	+													

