9. STATISTICAL METHODS

9.1 Calculation of the parameters of pharmacokinetics and pharmacodynamics

9.1.1. Pharmacokinetic parameters

Based on the calculated concentration values for the anti-IL-6 monoclonal antibody in the blood of each volunteer, the following pharmacokinetic variables will be estimated at time points specified in this protocol:

1. C_{\max} - maximum serum concentration of anti-IL-6 receptor antibody over the observation period.
2. t_{\max} - time to achieve maximum serum concentration (C_{\max}) of anti-IL-6 receptor antibody.
3. AUC_{0-1680} — the area under the concentration of anti-IL-6 receptor monoclonal antibody-time curve over the time interval from 0 to 1680 hours. AUC_{0-1680} will be calculated using the trapezoid method using the following formula, where C_p is the concentration of the drug BCD-089 in the blood at the time t_p in hours:

$$t_p \in \{0; 2; 8; 12; 24; 48; 72; 96; 120; 168; 240; 336; 504; 672; 1176; 1680\}_{p=1, \dots, 16}$$

4. $AUMC_{0-1680}$ - total area under the curve of the concentration of anti-IL-6 receptor monoclonal antibody multiplied by time over the time interval from 0 to 1680 hours. $AUMC_{0-1680}$ will be calculated using the following formula:

$$AUMC_{0-1680} = \sum_{p=2}^{16} \frac{(C_p * t_p + C_{p-1} * t_{p-1}) * (t_p - t_{p-1})}{2},$$

where C_p — concentration of anti – IL – 6

– receptor monoclonal antibody против рецептора ИЛ6

Translated from Russian to English, dated 06-Jul-2020

in the blood at t_p

$$t_p \in \{0; 2; 8; 12; 24; 48; 72; 96; 120; 168; 240; 336; 504; 672; 1176; 1680\}_{p=1, \dots, 16}$$

5. **Total clearance (Cl)** is a parameter that reflects the volume of test tissue, which is cleared from the anti-IL-6 receptor monoclonal antibody per unit of time and is determined by the ratio of the anti-IL-6 receptor monoclonal antibody dose (*DOSE*) to $AUC_{(0-1680)}$:

$$CL = \frac{DOSE}{AUC_{0-1680}}$$

6. **Mean residence time (MRT)** of the anti-IL-6 receptor monoclonal antibody molecule in the body will be calculated as the ratio of $AUMC_{0-1680}$ to AUC_{0-1680} :

$$MRT = \frac{AUMC_{0-1680}}{AUC_{0-1680}}$$

7. **Elimination constant** of the anti-IL-6 receptor monoclonal antibody (k_{el}) will be determined using the following formula:

$$k_{el} = \frac{1}{MRT}$$

8. **Half-life period** of the anti-IL-6 receptor monoclonal antibody ($T_{1/2}$) will be determined using the following formula:

$$T_{1/2} = \frac{\ln(2)}{k_{el}} = \ln(2) * MRT$$

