9. **The area under the concentration-time curve** for anti-IL-6 receptor monoclonal antibody **over the time interval from 0 to ∞ ($AUC_{0-\infty}$)**.

$$AUC_{0-\infty} = AUC_{0-1680} + \frac{C_{1680}}{k_{el}}, \text{ where}$$

Translated from Russian to English, dated 06-Jul-2020

C_{1680} – concentration of anti-IL-6 receptor antibody over the period equal to 1680 hours after the drug administration.

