9.1.2. Pharmacodynamical parameters

Based on the obtained concentrations of C-reactive protein, IL-6 and soluble IL-6 receptor in the blood of each volunteer, the following pharmacodynamic parameters will be calculated at the Protocol-specified time intervals:

1. C_{\max} – maximum blood concentration of C-reactive protein, IL-6 and soluble IL-6 receptor over the observation period.
2. t_{\max} – time to maximum blood concentration (C_{\max}) of C-reactive protein, IL-6 and soluble IL-6 receptor.
3. AUC_{0-1680} – the area under the concentration-time curve for C-reactive protein, IL-6 and soluble IL-6 receptor over the time interval from 0 to 1680 hours. AUC_{0-1680} is calculated using the trapezoidal method with the following formula:

$$AUC_{0-1680} = \sum_{p=2}^{16} \frac{(C_p + C_{p-1}) * (t_p - t_{p-1})}{2},$$

where C_p concentration of C – reactive protein, IL – 6 and soluble IL
– 6 receptor values

ИЛ6 in the blood at t moment of time t_p (hours),

$$t_p \in \{0; 2; 8; 12; 24; 48; 72; 96; 120; 168; 240; 336; 504; 672; 1176; 1680\}_{p=1, \dots, 16}$$

4. C_{\min} – minimum blood concentration of C-reactive protein, IL-6 and soluble IL-6 receptor over the observation period.
5. t_{\min} – time to minimum blood concentration (C_{\min}) of C-reactive protein, IL-6 and soluble IL-6 receptor.

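### The PK and PD sets have no late-sample condition, and the sample-count rules conflict at two missing samples, so a truncated area can be reported as AUC0-1680

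*Combined protocol and SAP*

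**What the plan says.** Section 9.7, repeated in the synopsis, defines the PK set as treated volunteers who "have had no more than two missing/lost/damaged blood serum samples for pharmacokinetics", who "had no more than two consecutive missing/lost/damaged samples", and "for whom a serum sample obtained before the test drug administration is available for the analysis". The PD set takes those who "have had no more than two missing/lost/damaged of whole blood and/or blood serum for pharmacodynamics studies", again with a pre-dose sample. In the same section, the immunogenicity set does require the Day 71 sample.

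Section 9.1 places samples at "0; 2; 8; 12; 24; 48; 72; 96; 120; 168; 240; 336; 504; 672; 1176; 1680" hours. In the Section 4.6.1 flowchart, the row "Day from the first injection" puts the last three at 28, 49 and 70 days (visits Day 29, Day 50 and Day 71).

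In 9.1.2 the PD AUC0-1680 "is calculated using the trapezoidal method with the following formula", and that sum runs to the sixteenth time point. The AUMC sum in 9.1.1 does the same. AUC0-inf in 9.1.1 adds a term in C1680, described as the "concentration of anti-IL-6 receptor antibody over the period equal to 1680 hours after the drug administration". Sections 7.1 and 7.2 instead define the area up to the last measured concentration, and state in brackets that in this study this is AUC0-1680.

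Two other sections count samples:
- Section 6.6 calls a volunteer non-compliant after more than one missed visit or more than two missed PK/PD samples. Section 5.3.1 allows such a volunteer to be replaced.
- Section 11.2 gives two or more missing PK/PD samples as an example of a probable major deviation. It requires anyone with a major deviation to be left out of the final PK/PD analysis.

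**The concern.** AUC0-1680 is a primary PK and PD quantity, and its last 1008 h rest on two samples. Losing the 2 h and 8 h samples changes the area little. Losing the last two removes more than half of the window. Section 9.7 treats the two cases alike.

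For a volunteer whose late samples are absent, the area as written in 9.1 either cannot be computed or stops early. The bracketed remark in 7.1 and 7.2 lets the shorter area carry the AUC0-1680 label. In 9.1.1 the error then passes into CL, MRT, k_el and T1/2. For CRP, a shorter area looks like suppression by the drug. Escalating cohorts start with three volunteers, so one case can move a cohort mean.

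**Working it through.** **Inputs.** The 16 sampling times come from 9.1.1 and 9.1.2, and the limits from 9.7, 6.6 and 11.2. The cohort size of three comes from the sample-size table in Section 9, which reproduces the planned maximum: 1 + 6 × (3 + 3) = 37. The plan gives no figure for the share of the window that may be unobserved.

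**Who passes, counting one sample per time point**

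| Case | 9.7 | 6.6 | 11.2 example |
|---|---|---|---|
| 1680 h absent | kept (1 ≤ 2) | compliant (1 visit, 1 sample) | not reached (1 < 2) |
| 1176 h and 1680 h absent, visits missed | kept (2 ≤ 2) | non-compliant (2 visits) | reached (2 ≥ 2): exclude |
| 1176 h and 1680 h tubes lost or damaged, visits attended | kept | compliant | unclear: lost or damaged tubes are named only in 9.7 |

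The PK limit on consecutive samples is also two, so it removes nobody whom the total limit keeps.

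**Unobserved time**
- 1680 h absent: (1680 − 1176)/1680 = 504/1680 = 30%.
- 1176 h and 1680 h absent: (1680 − 672)/1680 = 1008/1680 = 60%.

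With the pre-dose sample kept, 9.7 allows 15 × 14/2 = 105 pairs of missing samples. Of these, 91 leave no unobserved tail, 13 leave 504 h and one leaves 1008 h. That one pair is the pattern left by a volunteer who stops after Day 29.

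**PD, if truncated and the marker is flat.** The area scales with time.
- Stop at 1176 h: 1176/1680 = 0.70, a 30% fall. Mean of three: (2 + 0.70)/3 − 1 = −10%.
- Stop at 672 h: 672/1680 = 0.40, a 60% fall. Mean of three: (2 + 0.40)/3 − 1 = −20%.

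**PK, if truncated.** The readable text gives no half-life. I assume one compartment with first-order absorption, ka 0.15–0.4/day and half-lives of 5–28 days. Up to a constant, AUC(0–T) = (1 − e^(−ke·T))/ke − (1 − e^(−ka·T))/ka.

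Example with half-life 14 d and ka 0.25/day, so ke = ln 2/14 = 0.0495/day:
- T = 28 d: 15.15 − 4.00 = 11.15
- T = 49 d: 18.41 − 4.00 = 14.41
- T = 70 d: 19.57 − 4.00 = 15.57
- Ratios to 70 d: 11.15/15.57 = 0.716 and 14.41/15.57 = 0.926

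| Half-life | AUC0-672/AUC0-1680 | AUC0-1176/AUC0-1680 |
|---|---|---|
| 5 d | 0.91–0.97 | 0.99–1.00 |
| 14 d | 0.67–0.74 | 0.91–0.93 |
| 21 d | 0.57–0.64 | 0.85–0.88 |
| 28 d | 0.51–0.58 | 0.82–0.84 |

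The area is therefore 3–49% too low (stop at 672 h) or 0–18% too low (stop at 1176 h). At a ratio of 0.716, a mean of three with equal true values falls by 1 − (2 + 0.716)/3 = 9.5%, and that volunteer's CL = DOSE/AUC rises by 1/0.716 − 1 = 40%. At a 14 d half-life, truncation at 672 h shortens the calculated MRT, and so T1/2, by about 38%.

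**The case against.** The strongest objection is Section 11.2. A volunteer who leaves after Day 29 misses exactly two samples, which is the section's own example of a probable major deviation and leads to exclusion from the PK/PD analysis. He is also non-compliant under 6.6 and may be replaced under 5.3.1. A reader of 9.7 alone might infer that the plan simply keeps him. The documents do not support that: they point both ways. Nor does 9.7 ignore timing altogether, since it requires the pre-dose sample.

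This stands, but it does not close the gap. Section 11.2 offers examples, so classification is left to judgement. Replacement under 5.3.1 is optional, does not remove data from analysis, and is ruled out after withdrawal for safety. A single absent 1680 h sample does not reach the 11.2 threshold. If 11.2 meant PK and PD tubes from one draw to count separately, one missed Day 71 visit would reach two. The section does not say how to count, and a single lost PK tube would still pass.

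A second objection also stands: nothing readable says that a truncated area will be reported. Section 9.5 on missing data is redacted, the visit descriptions are redacted, and the Early Withdrawal Visit in 5.4 may include a draw. The biases above are what follows if truncation occurs, not a forecast.

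Third, escalation rests on 7-day toxicity, so no dose decision depends on AUC0-1680.

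**Conclusion.** The concern holds in this form. The PK and PD sets have no condition on late samples, although their primary area ends at 1680 h. Under the readable rules, a volunteer can be admitted with 30% of the window unobserved and no section objecting. At 60%, Sections 9.7 and 11.2 give opposite answers, and lost or damaged tubes fall between them. Because 7.1 and 7.2 equate area to the last measured concentration with AUC0-1680, reporting a truncated area under that label is a fair reading of the text, though not a certain one.

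The percentages of time are exact. The PD figures (30% or 60% in one volunteer, 10% or 20% in a mean of three) assume a flat marker and truncation. The PK figures (0–18% or 3–49%) assume truncation, one-compartment kinetics and the stated half-lives, and are small at short half-lives. The redacted 9.5 could reduce all of this.

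**What to change.** 1. Reconcile the counts in 9.7 (and the synopsis), 6.6 and 11.2. Use one threshold, one definition of a sample, and the same treatment of missing, lost and damaged samples. Section 11.2 must also allow a volunteer to be kept for some parameters and not others.
2. Make eligibility parameter-specific. AUC0-1680 and the parameters derived from it (CL, MRT, k_el, T1/2) count only if both the 1176 h and 1680 h samples are available. Otherwise keep the volunteer for Cmax, Tmax and AUC0-672. Requiring only the 1680 h sample is not enough: one linear trapezoid from 672 h to 1680 h overstates AUC by about 3–13% in the model above, against 0.5–4% on the full grid.
3. Align 9.1.1 with 7.1: AUC0-inf is the area to the last measurable time plus Clast/k_el, with k_el from the terminal phase. Remove the bracketed equation with AUC0-1680 from 7.1 and 7.2.
4. Report AUC0-672 for all cohorts as a sensitivity analysis for PK and PD. Dividing the PD area by follow-up time is no substitute. A marker at 20% of baseline to day 28 that recovers linearly by day 49 averages 0.20 to 672 h, but (28 × 0.2 + 21 × 0.6 + 21 × 1)/70 = 0.56 to 1680 h.

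The cost is wording only, with no new samples. An occasional volunteer is lost from AUC0-1680. The change should be made before concentration data are seen.

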	
Pharmacokinetics analysis will include data from volunteers who have received BCD-089 and have had no more than two missing/lost/damaged blood serum samples for pharmacokinetics and had no more than two consecutive missing/lost/damaged samples and for whom a serum sample obtained before the test drug administration is available for the analysis.
 
Pharmacodynamic analysis
 
Pharmacodynamics analysis will include data from volunteers who have received BCD-089 and have had no more than two missing/lost/damaged of whole blood and/or blood serum for pharmacodynamics studies, and for whom a serum sample obtained before the test drug administration is available for the analysis.
 
Immunogenicity analysis
 
Immunogenicity analysis will include data from volunteers who have received BCD-089 and have not had missing/lost/damaged serum samples taken on Days 1 and 71 of the study.
 
Report preparation
 
Preparation of the final study report will be performed after the end of the procedures for examination of the last participant.

--	--

Translated from Russian to English, dated 06-Jul-2020

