11.2. Investigator's adherence to protocol

No deviations from the Protocol are allowed during the study without prior written permission from JSC BIOCAD, except when necessary to prevent any immediate danger to the volunteer.

Protocol deviation is any change, discrepancy, or deviation from the study design or procedures of the study Protocol.

Any protocol deviation in the course of the clinical study must be registered and reflected in the study documents.

All protocol deviations are classified as major or minor deviations.

A minor deviation from the Protocol is an unforeseen and unintended event that occurred during the study and contradicts the requirements of the Protocol, which does not significantly affect the rights, safety and well-being of the volunteer or the consistency, accuracy and reliability of the study data.

A major deviation from the Protocol (or a protocol violation) is a deviation that may affect the rights, safety of a volunteer or the consistency, accuracy, and reliability of the study data.

Examples of probable major protocol deviations:

- A volunteer met study exclusion criteria but was not excluded;
- A volunteer received a prohibited concomitant medication;
- A volunteer was included in the study without meeting the eligibility criteria;
- Study procedures were conducted without obtaining a written informed consent from a volunteer;

Translated from Russian to English, dated 06-Jul-2020

- Volunteer’s indiscipline, non-compliance with restrictions during participation in the study (taking alcohol, drugs);
- Errors in selection of doses/route of administration/drug storage;
- Protocol violations that may be considered by the clinical trial monitor or study coordinator to have an impact on the safety of participants or the consistency and reliability of the study data;
- Missing two or more of the scheduled blood samples for analysis of pharmacokinetics/pharmacodynamics;
- Any violation of the confidentiality of information about study participants.

Information about major deviations should be presented to the Sponsor and the local ethics committee. In case of any major protocol deviations, the volunteer must be excluded from the final PK/PD data analysis.

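### Section 9.7 keeps volunteers with up to two missing PK or PD samples, 11.2 points to excluding them at two or more, and no visible text says which governs

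*Combined protocol and SAP*

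**What the plan says.** **Analysis sets.** Section 9.7, repeated in the synopsis, puts a dosed volunteer in the PK set if he had "no more than two missing/lost/damaged blood serum samples for pharmacokinetics and had no more than two consecutive missing/lost/damaged samples" and his pre-dose serum sample is available. The PD set has the same pre-dose condition and allows "no more than two missing/lost/damaged of whole blood and/or blood serum for pharmacodynamics studies". Each rule has its own count.

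**Compliance.** Section 6.6 makes a volunteer non-compliant on sample count only when more than two PK and PD samples were missed. A separate item covers missing more than one visit. Section 5.3.1 allows non-compliant volunteers to be substituted.

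**Deviations.** Under 11.2, "A major deviation from the Protocol (or a protocol violation) is a deviation that may affect the rights, safety of a volunteer"; the definition goes on to cover possible effects on data quality. A list follows, headed "Examples of probable major protocol deviations". It includes "Missing two or more of the scheduled blood samples for analysis of pharmacokinetics/pharmacodynamics" and also "Any violation of the confidentiality of information about study participants". The section then states: "In case of any major protocol deviations, the volunteer must be excluded from the final PK/PD data analysis".

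**Precedence.** No visible text ranks 9.7 against 11.2. Section 9.5 (missing data) is redacted, and so is 11.3 (the investigator's responsibility for adherence).

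**The concern.** Two sections decide whose concentrations enter the PK and PD analyses, and they set different limits. A volunteer can satisfy 9.7 in full and still match a listed example in 11.2, where classification as major leads to mandatory removal. Whether he is analysed then depends on which section the team follows and on how his deviation is classed.

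The AUCs are the primary PK and PD endpoints (7.1, 7.2), and the mandatory cohorts have three volunteers, or one in cohort 01, so a single decision is a large share of a dose level. The trial is open-label, and 9.3 places the analysis after all data are in. Nothing visible in 11.2 requires the classification to be made before concentrations are known.

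The 11.2 exclusion is also not tied to its purpose. Once a deviation is classed as major, PK/PD data are removed even if the deviation could not have changed a measured value. A confidentiality breach is the clearest listed case.

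**Working it through.** **1. Planned size.** From the table in 9.2 (sample size rationale): mandatory volunteers 1 + 6 × 3 = 19; maximum 1 + 6 × (3 + 3) = 37, which matches the synopsis. A cohort has more than three volunteers only after a DLT, substitution aside.

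**2. PK and PD counted separately.** Take samples of one type that were not drawn, with the pre-dose sample present.

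| Undrawn | 9.7 | 6.6 sample limit | 11.2 example |
|---|---|---|---|
| 0 | kept | within | no |
| 1 | kept | within | no |
| 2 | kept | within | yes |
| 3 | out | exceeded | yes |

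On this reading the only conflict is at exactly two.

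**3. PK and PD pooled in 6.6 and 11.2.** The wording of both sections allows one combined count. The formulas in 9.1.1 and 9.1.2 use the same 16 times for PK and PD, and Table 4 gives the PD samples their own label numbers. Assume that PK and PD are distinct samples and that both are missed at a given time point.

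| Time points missed | PK + PD | 9.7 (separate counts) | 6.6 | 11.2 example |
|---|---|---|---|---|
| 1 | 1 + 1 = 2 | kept | within | yes |
| 2 | 2 + 2 = 4 | kept | exceeded | yes |
| 3 | 3 + 3 = 6 | out | exceeded | yes |

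The conflict between 9.7 and 11.2 now begins at one missed time point. At two, the volunteer is also non-compliant under 6.6 and may be substituted under 5.3.1, while 9.7 still keeps him.

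**4. Is changing the number in 11.2 enough?** Suppose 11.2 read more than two. With separate counts, two is no longer a listed example and the conflict in step 2 goes. With a pooled count, two missed time points give 4 > 2, so the volunteer is still listed in 11.2 and still kept by 9.7. The counting unit has to be fixed as well as the threshold.

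**5. Size of one decision.** One of three is 33%, one of six is 17%, and in cohort 01 it is the whole cohort.

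**6. What is not touched.** Escalation in 4.2 rests on related grade 3-4 events in the first seven days. The safety analysis in 9.7 includes everyone dosed.

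**The case against.** The strongest reply is that there is no automatic contradiction. The 11.2 list gives probable examples, and a deviation is major only if it meets the general definition, so the team could class two missed samples as minor and apply 9.7. This is right as far as it goes: a reader might infer that 11.2 excludes everyone with two missed samples, and the text does not say that. What remains is that a numerical rule in 9.7 can be overridden by a judgement in 11.2, with no stated order and no stated timing.

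Second, the redacted 9.5 or 11.3 may settle precedence. That cannot be excluded and lowers confidence, although the visible limits in 9.7 and 11.2 would still differ.

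Third, 9.7 also counts lost and damaged samples, whereas 6.6 speaks of sampling that was missed and 11.2 of scheduled samples that are missing. The conflict is therefore claimed only for samples not drawn.

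Fourth, substitution may repair some cases: a volunteer who missed two visits is non-compliant under 6.6 whatever his sample count. But 5.3.1 does not say whether the replaced volunteer's data are analysed. With separate counting, two undrawn samples without two missed visits give no ground for substitution on sample or visit count.

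Two further inferences should not be drawn. The clause in the PK rule that he "had no more than two consecutive missing/lost/damaged samples" might look like a faulty exclusion rule. It is already implied by the total limit of two, so it excludes no one and alters no result. A reader might also think that the sets admit volunteers whose AUC to infinity cannot be computed because the last sample is missing. Section 7.1 describes a fitted terminal concentration, and 9.5 may address the case, so the documents do not establish that defect.

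**Conclusion.** The plan is wrong as written on this point. The limits in 9.7 and 11.2 conflict for undrawn samples: at exactly two if PK and PD are counted separately, and from one missed time point if 6.6 and 11.2 pool them. The statement that two undrawn samples lie within the 6.6 limit holds for the sample-count item, not for the item on missed visits. For two samples of one type with none of the other missed, it holds on either count; for two time points missed for both types, only under separate counting. Independently of the threshold, the 11.2 exclusion is broader than an analysis-set rule should be.

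The effect is one volunteer at a time: 33% of a three-person cohort's primary PK/PD data, unless he is substituted. How often this would happen cannot be judged, since the documents give no rate of missed samples. A reader might infer that dose escalation or the safety conclusions are at risk; they are not, because neither depends on the PK or PD sets. Confidence is moderate, given the redacted sections and the unclear counting unit.

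**What to change.** (a) State that 9.7 alone defines the PK and PD analysis sets. Use one missing-sample threshold in 9.7, the synopsis, 6.6 and 11.2, for example by changing 11.2 to more than two. Say in all four places that PK and PD samples are counted separately, and whether lost and damaged samples count.

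(b) In 11.2, replace the exclusion that follows any major deviation with exclusion only for deviations judged to affect the concentration data, with that judgement documented before concentrations are reviewed.

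(c) Optionally delete the redundant consecutive-samples clause from the PK rule, as tidying only.

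The cost is protocol wording. The downside is that some volunteers with two undrawn samples stay in with slightly sparser profiles. Two undrawn samples could still be classed as major under the general definition in 11.2, but under (b) they would lead to exclusion only if judged in advance to affect the concentration data.
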